2.8 Specific Drug Supply Requirements

It is required 300 vials of open label-Esmeron® (Rocuronium), 150 vials of open label-Sugammadex. Rocuronium and Sugammadex supplies should be sent from Zeulig to the study site in a bulk container, on a quarterly basis. Study drugs will be sourced locally and in original packaging according to the sponsor suggestion. Our research nurse will be responsible for storing, distributing the supplies as well as dispositions the unused supplies.

Calculations:

Base on surgical duration of 1- 2 hours, 1 vial of 0.6 mg/kg rocuronium (10mg/ml in 5 ml) will be required at induction and starting continuous infusion of 0.5 mg/kg/hour rocuronium will be used for maintenance.

Patient's distribution according to weight from 50-85 kg were estimated and used for calculation for all studied medications.

- 50 kg = 50% of sample population
- 65 kg = 20% of sample population
- 75 kg = 20% of sample population
- 85 kg = 10% of sample population

Moderate NMB: 1Vials/case for maintenance with continuous infusion of 0.5 mg/kg/h rocuronium during the case.

Deep NMB: 1 vial/case for maintenance with continuous infusion of 0.5 mg/kg/h Rocuronium during the case

	
(Total number of rocuronium for Deep and Moderate is required = 300 vials))
 
Sugammadex 4mg/kg or 2 mg/kg (200 mg /vials) will be given in Deep or Moderate rocuronium block arm, respectively. 2 vials are required for patients whose weight above 50 kgs in each arm. [Total number of Sugammadex required = 150 vials]
 
The actual cost of some anesthetic agents/equipment i.e. Propofol, TCI pump, infusion pump, End Tidal CO2 and BIS monitoring are able to be reimbursed as these may not be used as the routine practice. The maximum reimbursement of these is 319,000 THB for entire study.


2.9 Adverse Experience Reporting
	
All serious adverse experiences, regardless of relatedness to study medications will be collected throughout the course of study therapy and at least 7 days after the end of study therapy.
 
1. Recording Adverse Experiences
 
An adverse experience is defined as any unfavorable and unintended change in the structure, function, or chemistry of the body temporally associated with the use of the study's products, whether or not considered related to the use of the product. Any worsening (i.e., any clinically significant adverse change in frequency and/or intensity) of a preexisting condition which is temporally associated with the use of the product, is also an adverse experience.
 
Changes resulting from normal growth and development which do not vary significantly in frequency or severity from expected levels are not to be considered adverse experiences. Examples of this may include, but are not limited to, teething, typical crying in infants and children, and onset of menses or menopause occurring at a physiologically appropriate time.
 
Adverse experiences may occur in the course of the use of a product in clinical studies or within the follow-up period specified by the protocol, or prescribed in clinical practice, from overdose (whether accidental or intentional), from abuse, and from withdrawal.
 
Such events will be recorded at each examination on the Adverse Experience Case Report Forms/Worksheets.
 
2. Immediate Reporting of Adverse Experiences to the SPONSOR Serious Adverse Experiences
 
Any serious adverse experience, including death due to any cause, which occurs to any subject/subject entered into this study or within 14 days following cessation of treatment or within the established off therapy follow-up period for safety described in the protocol, whether or not related to the study product, must be reported within 24 hours to one of the individual(s) listed on the contact information page.
 
Additionally, any serious adverse experience considered by an investigator who is a qualified physician to be possibly, probably, or definitely related to the investigational product that is brought to the attention of the investigator at any time outside of the time period specified in the previous paragraph also must be reported immediately to one of the individuals listed on the sponsor contact information page found in the administrative binder. All subjects/subjects with serious adverse experiences must be followed up for outcome.
 
3. Responsibility for Reporting Adverse Experiences
 
All adverse experiences will be reported to regulatory agencies, IRB/IECs, in accordance with all applicable global laws and regulations.

2.12 Publication Plan	
Within 3 months after the study completion, we plan to submit an abstract of study to an international scientific meeting.
 
Within 6 months after the study completion, we plan to submit one manuscript to the International Journal related to Anesthesiology field.

Study Flow Chart

Study Procedures	Day 0	Day 1				Day2
Inclusion/Exclusion Evaluation	x					
Informed Consent	x					
Medical History Review	x					
OR* Surgeon Assessment		Q15 min				
OR Anesthesiologist Assessment		Q15 min				
OR TOF Watch [®] monitoring		Q15 sec				
OR PTC monitoring		Q 6 min				
OR Anesthetic routine monitoring		Q15 min				
OR residual blockade		At Extubation, 1,3,5,10minutes				
Study Procedures		Minutes				
		15	30	60	90	
PACU** routine monitoring		x	x	x	x	
PACU TOF Watch [®] monitoring		x	x	x	x	
PACU residual blockade assessment		x	x	x	x	
PACU readiness time to discharge		x	x	x	x	
Study Procedures		At arrival				(24 hours post PACU)
Ward residual blockade assessment				x		x

*OR =Operating Room, ** PACU = Post Anesthetic Recovery Room

Patient characteristics	Gr M (N =48)	Gr D (N=49)
Gender		
Female	20 (41.7%)	23 (46.9%)
Male	28 (58.3%)	26 (53.1%)
ASA physical status		
1	18 (37.5%)	19 (38.8%)
2	30 (62.5%)	30 (61.2%)
Airway type		
Tracheal tube	27 (56.3%)	25 (51.0%)
Tubeless	17 (35.4%)	21 (42.9%)
Combination	4 (8.3%)	3 (6.1%)
AGE (years)	43.5 (11.78)	42.31(13.28)
BMI (kg/m²)	23.75(3.66)	22.07(5.15)
Operation time (minutes)	53.73(73.99)	78.84 (186.97)
Anesthetics		
Fentanyl (µg)	75.96 (54.0)	82.4(52.13)
Propofol (mg)	465.6 (257.26)	481.88 (206.56)
Rocuronium (mg)	38.36 (16.51)	53.65 (16.38)
Sugammadex (mg)	132.99 (35.7)	237.53 (37.66)

Data were presented in number (%) or mean(SD)

Intraoperative outcomes	Gr M	Gr D	p-value
Surgical Grading			
Clinically acceptable	43 (89.6%)	49(100%)	
Not acceptable	5(10.4%)	0	0.027*
Surgeon's compliant	9(18.7%)	5 (10.2%)	0.231
Cough	34(70.8%)	16(32.7%)	<0.001*
Total additional doses of Rocuronium	23 (47.9%)	10 (20.4%)	0.005*

Recovery parameters	Gr M	Gr D	p-value
Time to T4 (seconds)†	60(60-120)	60(60-120)	0.497
Time to TOF0.9 (seconds)‡	180(120-240)	120(109-180)	0.034*
PORC at PACU (number of patients)§	0	0	-
Time to ALD≥9 (minutes)¶	33(18-48)	27[14-42]	0.253
Nausea/Vomiting (number of patients)	0(0%)	4(8.2%)	0.117

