We will describe the data distribution of each collected variable. We will characterize subjects in both groups by demographics, comorbidities, clinical characteristics i.e. neuromuscular weakness grading, and distribution of ASA Classification pattern. Categorical variables will be summarized by frequency and percent while continuous variables will be summarized by the mean, median, standard deviation, and range.

Clinical Outcomes:

The data analysis will be based on the intent-to-treat approach. Categorical variables will be compared using the Fisher's exact test while continuous variables will be compared using the student's t-test or Mann-Whitney U test, depending on the sample distribution.

The level of statistical significance for all analyses is set at 0.05. All comparisons will be made using an alpha level of 0.05.

Sample Size: By using 80% power and 1-sided $\alpha=0.05$, we performed sample size calculation for the proportional outcome. Based on data from the BLISS study¹², the proportion of patients with a score of Excellent on the Surgical Rating Score (SRS) among subjects who receive deep NMB with Rocuronium is approximately 99%, while this proportion for patients who received moderate NMB with atacurium followed by mivacurium was lower (82%). The calculated subjects is required 36 subjects per arm. Since we expect 13% of withdrawal from the study¹³, we need to inflate the total sample size to 80 subjects (40 subjects per arm)

Efficacy Analysis:

1. Primary Efficacy endpoints:

The Proportion of patients who have a surgical conditions score of excellent (total score = 8-9) will be compared between the Moderate NMB and Deep NMB groups.

2. Secondary outcome

- 1) The proportion of patients who are ready to be discharged from post- operative care, defined as Modified Aldrete's score ≥ 9 , at 0, 15, 30,60, 90 minutes after reach of TOF > 0.9 will be summarized.
- 2) The proportion of patients who are ready to be discharged from the operating room, defined as TOF > 0.9 at time of tracheal extubation, at 1, 3, 5, 10 minutes after finish of Procedures will be summarized.
- 3) The frequency of patients with clinical signs of early recovery during Endolaryngeal Procedures will be compared between the deep NMB and Moderate NMB arms.

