2.7 Statistical Analysis and Sample Size Justification	
The principle investigator will be responsible for analyzing the study data. Since the research team is not blinded to the muscle relaxant used and the level of NMB, either the attending anesthesiologist or the research assistant is responsible for both the administration of the muscle relaxant and the degree of NMB. The attending anesthesiologist is also not blinded. He or she will not discuss the NMB with the surgeon or the research team. After the surgery has finished, subjects who receive rocuronium will be reversed with sugammadex 4 mg/kg or 2 mg/kg. Again, this will be known by the attending anesthesiologist only and will be blinded to surgeon and Anesthesiologist and Otolaryngologist Experts who will rate the surgical conditions..
 
Variables/Time Points of Interest:
 
1. Primary outcome:
 
1) Proportion of patients who have a surgical conditions score of excellent,
 
 • Surgical conditions will be rated using a four-point surgical rating scale (SRS) by the Surgeon right after operation. • The SRS has been modified from Intubating score¹⁰. • There are three variables, which are ease of laryngoscopy, condition of the vocal cords and the Reaction to insertion of the endoscopic tube and cuff inflation. These are scored on a four-point scale (0-3) and the total score is a sum of each component to give an overall Surgical Conditions score for each patient. • The assessment is based on the time point right after operation. • A total score of 8-9 was considered excellent, 6-7 good, 3-5 poor and 0-2 bad; good and excellent were taken as clinically acceptable. 
2. Secondary outcomes:
 
1) Proportion of patients who are ready to be discharged from post-operative care, defined as Modified Aldrete's score ≥ 9, at 0,15, 30, 60,90 minutes after reach of TOF > 0.9.
 
 • Modified Aldrete's score: A score ≥ 9 is required for discharge. 
2) Proportion of patients who are ready to be discharged from operating room, defined as TOF > 0.9 at time of tracheal Extubation, 1,3,5, 10 minutes after finish of a procedure.
 
3) Frequency of clinical signs of early recovery during Endolaryngeal Procedures.

Clinical signs of early recovery:

- 1) Airway pressure alarm
- 2) Movement of Vocal cords on Laryngeal Video monitor
- 3) Movement of the abdomen
- 4) Change of End Tidal CO₂

3. Other outcomes:

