- 1) Proportion of patient at risk of of Post-Operative Residual Curarization (PORC) (TOF ration < 0.9) at 1,3,5,10 minutes after finish of a procedure and at 0, 15,30, 60, 90 minutes during Post-Operative Care Unit stay.
- 2) Time to readiness to discharge from Post-operative Care Unit which is time from Post-operative Care Unit (PACU) admission to reach “acceptable” score of Post-operative discharge score.
- 3) Time readiness to discharge from operating room, which is time from finish of procedures to train of Four ratio > 0.9
- 4) Proportion of patients who have a surgical conditions score in each category (Excellent, good, fair and poor).
 - Surgical conditions will be rated using a four-point surgical rating scale (SRS) by an anesthesiologist. (not attending physicians) every 15 minutes and every change seen or surgeon’s complaint.
 - The SRS will be also rated by an expert anesthesiologist and expert ENT surgeon from VDO recorder every change seen at a vocal cord.
- 5) Intubating condition in patients who has endotracheal insertion. This will be assessed by anesthesiologist right after finishing intubation by using the same score of endolaryngeal surgical condition

Study Variables during anesthesia

Endolaryngeal surgical condition¹⁰:

During the endolaryngeal Procedures, a surgeon scores the surgical working conditions right after the end of procedures. We adapted the Intubation Condition criteria^{11,12} included three variables:

- 1) jaw relaxation and resistance to laryngoscopy blade (laryngoscopy component)
- 2) the position and movement of vocal cords (vocal cord component)
- 3) coughing (reaction to endolaryngeal and endobroncheal Procedures component)

Evaluation of Endolaryngeal/Endobroncheal surgical conditions¹²

Variable assessed	Clinically acceptable		Not clinically acceptable	
	Excellent = 3	Good = 2	Poor = 1	Impossible = 0

Laryngoscopy[‡] 
 • Jaw relaxation • Resistance to blade 	Easy 
 • Relaxed • None 	Fair 
 • Not fully relaxed • Slight 	Difficult 
 • Poor relaxation • Active 	Impossible 
 • No relaxation

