Vocal cord 
 • Position • Movement 	
 • Abducted • None 	
 • Intermediated • moving 	
 • Closing 	
 • Closed
Reaction to insertion of the endoscopic tube and cuff inflation 
 • Diaphragmatic movement • coughing 	
 • None • None 	
 • Slight^β movement • None 	
 • Vigorous movement^θ • Sustained coughing^θ 	
 • Bucking • Severe coughing

‡Laryngoscopy

Easy: jaw relaxed, no resistance to blade insertion

Fair: jaw not fully relaxed, slight resistance to blade insertion

Difficult: poor jaw relaxation, active resistance of the patient to laryngoscopy.

β One to two weak contractions or movement for less than 5 s.

θ More than two contractions and/or movement for longer than 5 s.

Endolaryngeal surgical site conditions⁹:

Excellent ;Score = 8-9

Good ;Score = 6 -7

Fair ;Score = 3-5

Poor ;Score =0-2

Surgical rating

During the laryngoscopic Procedures, the surgical condition is scored by the surgeon using a four-point SRS right after the Procedures. To reduce variability in the surgical rating, all surgeries are performed by a single surgeon at each institute.

The surgical rating scores (SRS) condition at 15-minute intervals will be recorded and rated by an anesthesiologist during the Procedures. In case of a sudden change in surgical conditions, additional scores are obtained. If conditions are poor (score 0 or 2), muscle relaxation is increased according to protocol.

Before commencing the study, both the surgeon and the anesthesiologists will receive training in how to use and implement the specific study Procedures and how to rate the surgical condition score.

Moreover, the first five Procedures performed in conformance with this protocol will not be used for data analysis; thus, the Procedures will be practiced five times before data collection starts.

Intubation score

At the end of intubation, the intubation condition is scored by anesthesiologist by using the same score of endolaryngeal surgical condition

Video images

The video images will be collected from the camera connected to endoscope placed

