Before discharging from Post-Operative Care Unit, patients will be assessed “time readiness to discharge from PACU” by evaluating Modified Aldrete recovery score. The score will be measured at least 15 minutes interval.

MODIFIED Aldrete recovery score¹⁴

Parameter	Description of patient	Score
Activity level	Moves all extremities voluntarily/on command	2
	Moves 2 extremities	1
	Cannot move extremities	0
Respirations	Breathes deeply and coughs freely	2
	Is dyspneic, with shallow, limited breathing	1
	Is apneic	0
Circulation (blood pressure)	Is 20 mm Hg > preanesthetic level	2
	Is 20 to 50 mm Hg > preanesthetic level	1
	Is 50 mm Hg > preanesthetic level	0
Consciousness	Is fully awake	2
	Is arousable on calling	1
	Is not responding	0
Oxygen saturation as determined by pulse oximetry	Has level >90% when breathing room air	2
	Requires supplemental oxygen to maintain level >90%	1
	Has level <90% with oxygen supplementation	0

Maximum total score is 10; a score of ≥ 9 is required for discharge.

- Main goals are controlling postoperative pain, controlling nausea and vomiting, and reestablishing normothermia prior to discharge
- Majority of patients can meet discharge criteria within 60 minutes in the PACU, no demonstrable benefit from a mandatory minimum duration of PACU care
- Outpatients who meet the above discharge criteria may be “fast-tracked” to phase 2 recovery, similarly inpatients who meet the same criteria may be transferred directly from the OR to their ward. This is required less extensively monitoring.

Statistical Methods:

All statistical analysis will be performed by STATA or SPSS, depends on availability.

Baseline Patients Characteristics:

We will describe the data distribution of each collected variable. We will characterize subjects in both groups by demographics, comorbidities, clinical characteristics i.e. neuromuscular weakness grading, and distribution of ASA Classification pattern. Categorical variables will be summarized by frequency and percent while continuous variables will be summarized by the mean, median, standard deviation, and range.

Clinical Outcomes:

The data analysis will be based on the intent-to-treat approach. All comparisons will be made using an alpha level of 0.05

1. Primary Efficacy endpoints:

The Proportion of patients who have a surgical conditions score of excellent will be compared between the Moderate NMB and Deep NMB groups using Fisher’s Exact test

2. Secondary outcome

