Based on data from the BLISS study¹⁵, the proportion of patients a with a score of Excellent on the Surgical Rating Score (SRS) among subjects who receive deep NMB with Rocuronium is approximately 99%, while this proportion for patients who received moderate NMB with atacurium followed by mivacurium was lower (82%)..

By using 80% power and 1-sided $\alpha=0.05$, we performed sample size calculation by using the following formula.

For the proportion outcomes

$$n = \frac{2(\bar{p})(1 - \bar{p})(Z_{\beta} + Z_{\alpha})^2}{(p_1 - p_2)^2}$$

All expected primary outcome, secondary outcomes and calculated sample sizes are shown in the following table

	Deep NMB	Mode rate NMB	Sample size
Primary outcome			80% Power
- Proportion of Excellent	99%	82%	36/arm

Since we expect 13% of withdrawal from the study¹⁶, we need to inflate the total sample size to **80 subjects (40 subjects per arm)**.

As mentioned in the earlier session, the first five Procedures performed in conformance with this protocol will not be used for data analysis; thus, the Procedures will be practiced five times each center before data collection starts.

Therefore, the total enrolled patients are 110 patients.

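### The results tables test surgical grading as acceptable versus not acceptable (p = 0.027); the primary endpoint, excellent (8-9), is not shown and cannot be derived from them

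*Combined protocol and SAP*

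**What the plan says.** The plan is consistent about its primary endpoint.

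- **Endpoint.** The synopsis (Efficacy Analysis) sets the comparison of the two arms in the sentence that begins "The Proportion of patients who have a surgical conditions score of excellent (total score = 8-9) will be compared between the Moderate NMB".
- **Rater and time.** Section 2.7, Primary outcome: "Surgical conditions will be rated using a four-point surgical rating scale (SRS) by the Surgeon right after operation".
- **Test.** Section 2.7, Clinical Outcomes, assigns Fisher's exact test to this comparison, in the sentence that begins "The Proportion of patients who have a surgical conditions score of excellent will be compared between the Moderate NMB and Deep NMB groups using".
- **Sample size.** The only row of the sample size table in Section 2.7 is "Proportion of Excellent", 99% deep versus 82% moderate, 36 per arm.

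Section 2.7 also describes a wider class. After giving 8-9 as excellent and 6-7 as good, it adds that "good and excellent were taken as clinically acceptable". This describes the scale; it is not listed as a primary, secondary or other outcome. Under Other outcomes the section lists "Proportion of patients who have a surgical conditions score in each category (Excellent, good, fair and poor").

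The tables after the Study Flow Chart report 48 moderate and 49 deep patients. Under Surgical Grading the Intraoperative outcomes table has two rows: "Clinically acceptable", 43 (89.6%) versus 49 (100%), and not acceptable, 5 (10.4%) versus 0, with a starred p-value of 0.027. It does not name the rater. No table gives the excellent count or the total scores.

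**The concern.** The trial was designed and powered on a cut at 8 points, while its tables are cut at 6. The starred 0.027 is the only between-arm test of surgical grading in the supplied document, so it is the figure a reader will find when looking for the answer to the primary question. If it is read that way, the trial's main conclusion rests on a comparison that the plan did not name as an outcome, and the comparison that the plan did name stays unseen.

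**Working it through.** **Reproducing the reported figure.** Inputs from the Intraoperative outcomes table: not acceptable 5 of 48 (moderate) and 0 of 49 (deep). The rows add up to the arm sizes (43 + 5 = 48; 49 + 0 = 49). With five not-acceptable patients among 97, the probability that all five fall in the moderate arm is

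C(48,5) / C(97,5) = 1,712,304 / 64,446,024 = 0.0266.

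The opposite extreme, all five in the deep arm, has probability C(49,5) / C(97,5) = 1,906,884 / 64,446,024 = 0.0296. This exceeds 0.0266, so the usual two-sided Fisher test does not add it. The two-sided p is therefore 0.0266, which rounds to the printed 0.027. The printed value is Fisher's exact test on acceptable versus not acceptable.

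**Is acceptable the same class as excellent?** Each of three components scores 0-3. Excellent (8-9) needs 3+3+3 or 3+3+2 in some order. Acceptable (6-9) also admits totals of 6 and 7, such as 2+2+2 or 3+2+2. The scoring grid in Section 2.7 also uses acceptable at component level, for scores of 2 or 3. If the results row means that every component was at least 2, excellent is still a proper subset, because 2+2+2 qualifies as acceptable but not as excellent. On either reading the row tests a wider class.

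**What the row implies for excellent.** Assume that the row is the surgeon's end-of-operation rating. Then excellent is at most 43/48 (89.6%) in moderate and at most 49/49 (100%) in deep. The row sets no lower limit, so the excellent proportions and the p-value are not determined.

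**Sensitivity close to the reported counts.** Suppose that all 43 acceptable moderate patients were excellent and that one deep patient was good. There are then six not-excellent patients, five moderate and one deep. With C(97,6) = 988,172,368:

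- five moderate, one deep: C(48,5) × 49 / C(97,6) = 0.0849
- six moderate: C(48,6) / C(97,6) = 0.0124
- six deep: C(49,6) / C(97,6) = 0.0142, counted because it is below 0.0849
- one moderate, five deep: 0.0926, not counted because it is above 0.0849

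Two-sided p = 0.0849 + 0.0124 + 0.0142 = 0.1115. One-sided p = 0.0849 + 0.0124 = 0.0973. Both exceed 0.05, so the plan's silence on the sidedness of the analysis (the sample size used one-sided 0.05) does not affect this example.

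Illustrations only, all compatible with the printed row:

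| Excellent, moderate | Excellent, deep | Two-sided Fisher p |
|---|---|---|
| 43/48 (89.6%) | 49/49 (100%) | 0.027 |
| 43/48 (89.6%) | 48/49 (98.0%) | 0.11 |
| 30/48 (62.5%) | 35/49 (71.4%) | 0.39 |
| 20/48 (41.7%) | 40/49 (81.6%) | 0.00006 |

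The primary p-value could be larger or smaller than 0.027.

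**The case against.** The strongest reply is that the plan has no defect here. Endpoint, rater and test are clear, and the tables neither call 0.027 primary nor claim to be complete. Symbols in the recovery table have no footnotes in the supplied text, and figures are not shown, so an excellent row may exist elsewhere. All of this stands, and it limits the point to what the supplied tables show. It does not make 0.027 the primary result, and nothing else in the document fills the gap.

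The four-category breakdown also carries little weight. Section 2.7 lists it under Other outcomes, with an anesthesiologist and video experts as raters, and treats those ratings descriptively. Its absence from a short set of tables is not a departure from the plan.

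Stronger readings that the documents do not support:

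- **That the endpoint was switched or the primary analysis omitted.** A reader might infer this from the missing row. An unlabelled and possibly partial set of tables cannot show it.
- **That the cough row (34/48 versus 16/49) caps the number excellent.** In the Section 2.7 grid, scores 3 and 2 require no cough and score 1 is "Sustained coughing", so a brief cough has no cell. The cough row gives no timing, definition or rater, whereas the grid component concerns the reaction to tube insertion and cuff inflation. If acceptable is meant at component level, coughs scored 1 or lower would make patients not acceptable, yet only 5 and 0 are.
- **That the range of permitted counts says which result is likely.** It shows only that excellent cannot be derived; the counts are not equally plausible.

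**Conclusion.** The point holds in a limited form. The supplied tables depart from the plan by reporting a wider class than the primary endpoint. The printed p = 0.027 (0.0266 recomputed) is not the primary result, and the excellent counts cannot be derived. No size can be given for the primary effect. The nearest alternative, one deep patient good instead of excellent with moderate at its maximum, gives p = 0.11, so significance on acceptable does not carry over automatically to excellent. The upper limits of 43/48 and 49/49 assume that the row is the surgeon's end-of-operation rating, which the table does not state. That 0.027 does not test the primary endpoint needs no such assumption. This should be fixed before the tables are used to answer the primary question.

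**What to change.** Report excellent (8-9) versus not excellent by arm, from the surgeon's end-of-operation rating, with Fisher's exact test, and label it as the primary result. If it is already reported elsewhere, place it in this table or refer to it. Label acceptable versus not acceptable as non-primary, say whether it is defined on the total or on the components, and name its rater. Four-category counts by arm, with the rater named, would be a useful descriptive addition but are optional.

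The cost is a re-tabulation of scores that the plan already requires, with no new data. The downside is that the p-value reported for surgical conditions may be less favourable than 0.027.
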